6.4.2.4 Treatment-Emergent Adverse Events

Adverse events will be considered treatment-emergent adverse events (TEAE) according to the following algorithm, and will be applied to the Full Analysis Set population:

- If the complete onset date of an AE is known, then:
 - If the AE onset date is prior to initial treatment date, then the AE will not be considered treatment-emergent.
 - If the AE onset date occurs on or after initial treatment date, then the AE will be considered treatment-emergent.
- If the AE onset date is partially known, then:
 - If day is unknown, and month/year occur on or after the first enema month/year, then the AE will be considered treatment-emergent. Otherwise, the AE will not be considered treatment-emergent.
 - If month/day is unknown, and year occurs on or after first enema year, then the AE will be considered treatment-emergent. Otherwise, the AE will not be considered treatment-emergent.
- If the onset date of an AE is unknown, then the following rules will apply:
 - If the AE resolution date is after the initial treatment date or ongoing, then the AE will be considered treatment-emergent.
 - If the AE resolution date is before the initial treatment date, then the AE will not be considered treatment-emergent.

- If both the onset and resolution dates are unknown, then the AE will be considered treatment-emergent.

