#### 4.3 Subject Recruitment and Screening

Subjects are recruited by qualified and trained site personnel when they are identified as experiencing either a) at least two recurrences of CDI after a primary episode (i.e., at least three episodes) and have completed at least two rounds of standard-of-care oral antibiotic therapy or b) had at least two episodes of severe CDI resulting in hospitalization. Potential subjects are to be fully informed as to this study's purpose, requirements, anticipated risks, etc., and are to be given the chance to review the informed consent form and receive satisfactory answers to all questions. Subjects must then sign the study-specific, IRB/REB-approved Informed Consent Form and HIPAA Form (if applicable), which is the point of study enrollment.

Subjects are eligible to receive study treatment upon confirmation that they have met all inclusion/exclusion criteria listed in Sections 4.1 and 4.2. Subjects must discontinue their antibiotics for 24-48 hours prior to receiving the first study enema.

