### 7.1.5 Adverse Event Reporting to the Sponsor

Sites are required to record and report all adverse events to Rebiotix via entry on the Adverse Event eCRF in the study database within **ten (10)** working days of discovery unless it is an SAE or serious suspected adverse reaction. Serious adverse events (SAEs) and serious suspected adverse reaction events must be reported within **three (3)** working days of discovery by recording them in the study database. Adverse event information is collected from the time the subject signs the Informed Consent Form and HIPAA Form (if applicable) through study termination. All adverse events, including serious adverse events and the new onset of chronic diseases, will be collected through 12 months; serious adverse

events and the new onset of chronic diseases will be collected through 24 months after completion of study treatment. [REDACTED]

[REDACTED]  
[REDACTED]  
[REDACTED] Neither a condition, hospitalization, prolonged hospitalization, nor surgery are reported as an adverse event if the hospitalization or prolonged hospitalization is for diagnostic or elective surgical procedures for a preexisting condition. Surgery should not be reported as an outcome of an adverse event if the purpose of the surgery was elective or diagnostic and the outcome was uneventful. Reoccurrence of CDI is *not* to be reported as an AE or SAE unless hospitalization  $\geq 24$  hours is required to treat it. If hospitalization is not required, it is to be recorded on the Follow-up eCRF and CDI History and On-study Episodes eCRF and reviewed as a component of efficacy assessment. If hospitalization for recurrent CDI is required, it is to be reported as an SAE within 3 working days of discovery in the database and on the CDI History and On-study Episodes eCRF. [REDACTED]

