6.4.2 Adverse Events

An adverse event (AE) is any untoward medical occurrence associated with the use of RBX2660, whether or not the event is considered product-related. Pre-existing conditions that worsen in frequency, intensity or character of the condition during study participation will be recorded as an AE. Adverse events will be recorded for each subject from the day of enrollment through the 12-month phone call. Serious adverse events (SAEs) and the new onset of chronic diseases will be recorded for each subject from the day of enrollment through the duration of the study.

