8.6.1 Adverse Events

A summary of adverse events, TEAEs, non-serious TEAEs, and serious TEAEs will be summarized using counts of the number of events and frequencies (counts and percentages) of the number of subjects in the Full Analysis Set. The frequency of each preferred term (PT) within the primary system organ class (SOC) as well as overall primary SOC frequency will be presented. A subject with multiple events coded to the same PT within a primary SOC will be counted only once for the PT within the primary SOC. Likewise, a subject with multiple events coded to the same SOC will be counted only once within the SOC. Adverse events and serious adverse events will also be summarized by onset timepoint by system organ class (SOC) and preferred term (PT): [REDACTED]

[REDACTED]

[REDACTED] Adverse events will be counted in the interval in [REDACTED]

which the start date of the event occurs. For subjects with multiple instances of the same event, the events will be counted once within each interval that the event starts.

An overall summary of AEs will present the frequency of all TEAEs, serious TEAEs, and TEAEs leading to death for the Full Analysis Set, as well as the frequency of the following for the RBX2660 treatment group:

- TEAEs related to RBX2660
- TEAEs related to enema procedure
- TEAEs related to *C. difficile* disease
- TEAEs related to a pre-existing condition
- Serious TEAEs related to RBX2660
- Serious TEAEs related to the enema procedure
- Serious TEAEs related to *C. difficile* disease
- Serious TEAEs related to a pre-existing condition.

Frequency of occurrence and number and percentage of subjects experiencing an event will be presented by SOC and PT using the Safety Population for the following:

- TEAEs by maximum severity
- TEAEs by relatedness to RBX2660
- TEAEs by relatedness to *C. difficile* disease
- TEAEs by relatedness to enema procedure
- TEAEs by relatedness to pre-existing condition
- Serious TEAEs
- Serious TEAEs by maximum severity
- Serious TEAEs by relatedness to RBX2660
- Serious TEAEs by relatedness to *C. difficile* disease
- Serious TEAEs by relatedness to enema procedure
- Serious TEAEs by relatedness to pre-existing condition

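### The TEAE rule has no worsening clause, so an AE dated between consent and the first enema stays non-emergent even if it becomes severe or serious after RBX2660

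*SAP*

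**What the plan says.** SAP 6.4.2.4 (Treatment-Emergent Adverse Events) gives a date-based algorithm. For a complete onset date: "If the AE onset date is prior to initial treatment date, then the AE will not be considered treatment-emergent". For incomplete dates it leans the other way:

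- Day missing: "If day is unknown, and month/year occur on or after the first enema month/year, then the AE will be considered treatment-emergent".
- Month and day missing: "If month/day is unknown, and year occurs on or after first enema year, then the AE will be considered treatment-emergent".
- Onset missing altogether: "If the AE resolution date is after the initial treatment date or ongoing, then the AE will be considered treatment-emergent".
- Onset and resolution both missing: treatment-emergent.

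No branch mentions a later change in severity, frequency or seriousness.

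Recording starts before dosing. Protocol 7.1.5: "Adverse event information is collected from the time the subject signs the Informed Consent Form". SAP 6.4.2: "Adverse events will be recorded for each subject from the day of enrollment through the 12-month phone call".

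Protocol 7.1.4 and SAP 6.4.2 both require a pre-existing condition that worsens during the study to be recorded as an AE. Protocol 7.1.4 and SAP 6.4.3.3 define such a condition as one already there when the study starts, noted at screening or baseline.

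SAP 8.6.1 then builds its severity, relatedness and serious-event tables by SOC and PT on TEAEs only, for example "TEAEs by maximum severity".

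**The concern.** The period between consent and first enema is not event-free. Subjects have recently had CDI and are on or starting antibiotics for it. Protocol 4.3 adds a washout: "Subjects must discontinue their antibiotics for 24-48 hours prior to receiving the first study enema". SAP 8.3 allows baseline assessments up to 30 days before treatment. An unsolicited event could begin as mild in this period and become severe or serious after dosing. Its date of onset then settles its classification, and the post-dose grade, relatedness and seriousness never reach the TEAE tables.

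This matters because safety is the first secondary objective and SAP 8.6.1 plans no inferential AE statistics. Protocol Appendix 1, A1 also rules out comparing safety with the historical controls. The descriptive TEAE tables therefore carry most of the severity and relatedness picture. For the events concerned, the error runs in one direction, towards understatement.

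**Working it through.** The plan states no figure on this point and no arithmetic applies. The check is to take one kind of event, an AE that truly began before the first enema and worsened after it, and follow it through every route in SAP 6.4.2.4.

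| Information on the AE record | Result under the SAP |
|---|---|
| 1. Complete onset date, before first enema | Not a TEAE |
| 2. Day missing; month earlier than first-enema month | Not a TEAE |
| 3. Day missing; same month and year as first enema | TEAE |
| 4. Month and day missing; earlier year | Not a TEAE |
| 5. Month and day missing; same year | TEAE |
| 6. Onset missing; ongoing, or resolved after first enema | TEAE |
| 7. Onset and resolution missing | TEAE |
| 8. Pre-existing condition whose worsening is entered as an AE dated at the worsening, after first enema | TEAE |

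Routes 1, 2 and 4 lose the event.

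The treatment of dates is uneven. Suppose an AE is known to have begun the day before the first enema and becomes serious afterwards. It is excluded by route 1. If its onset date is missing and it is ongoing, it is included by route 6. The rule is cautious when the onset date is missing and not when it is known.

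Route 8 closes the gap only in part:

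- An AE that starts after consent is not clearly a condition present at the start of the study.
- No visible text says the AE is dated at the worsening. If it takes the condition's own earlier onset date, it falls into route 1.
- A condition that worsens during screening becomes an AE with a pre-dose onset. If it worsens again after the enema, route 1 still applies.

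Where an event lost by routes 1, 2 or 4 still appears:

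| Output | Event shown? | What is missing |
|---|---|---|
| All-AE summary by SOC and PT (SAP 8.6.1) | Yes | No visible breakdown by severity or relatedness |
| AE and SAE listings (8.6.1) | Yes | Not tabulated |
| AEs and SAEs by onset interval (8.6.1) | Yes | Assigned by start date, so before dosing |
| Diary shift tables (8.6.2.1) | Only the 11 solicited symptoms, through day 7 after the last enema | No relatedness or seriousness |
| Major complications of CDI (8.6.2.2) | Only if it is one of those complications | Other events |
| Overall TEAE summary, including serious TEAEs and TEAEs leading to death (8.6.1) | No | The event |
| TEAE and serious-TEAE tables by severity and relatedness (8.6.1) | No | The event |

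**The case against.** The strongest case on the other side has four parts.

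1. **Pre-existing conditions may absorb these events.** Protocol 6.5 puts the baseline visit on the day of the first enema and has pre-existing conditions documented there. A symptom that arose in screening could be entered as pre-existing, and its later worsening recorded as a new AE. This is a possible reading, but the definition in terms of the start of the study pulls against it, and the dating of the new AE is unstated. It leaves an ambiguity and does not close the gap.

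2. **The diary already measures worsening.** Abdominal pain, diarrhea, nausea, rectal symptoms and other solicited symptoms have a pre-treatment baseline and shift tables. This stands for those 11 symptoms around dosing. It does not cover unsolicited events, worsening after day 7 following the last enema, relatedness or seriousness, whereas AEs are collected to 12 months and SAEs to 24.

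3. **The events stay in the report.** They do, in the all-AE summary and the listings. A reader might infer that they vanish from the safety output; the documents do not support that.

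4. **Site practice is unknown.** Parts of Protocol 7.1.5 and of the SAP's AE sections are blacked out, and eCRF completion instructions are not among the documents. Sites may already be told to open a new record on worsening. This limits what can be said about the data as collected, but the visible algorithm would still not reflect such an instruction.

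A reader might also infer that every event beginning before the first enema is excluded. Routes 3, 5, 6 and 7 show otherwise.

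**Conclusion.** The gap is real but narrow. An AE with a complete onset date between consent and first enema, or a partial date in an earlier month or year, is not treatment-emergent even if it becomes more severe or serious after RBX2660. It leaves the TEAE and serious-TEAE tables by severity and relatedness, and the onset-interval tables put it before dosing.

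The number of subjects affected cannot be derived. The documents give no rate of AEs in screening or washout, no proportion that worsen, and no account of how sites record worsening. Any count would be a guess. For scale only: if 150 subjects are treated, each subject missed lowers the corresponding percentage by at most 1/150 = 0.67 percentage points. A subject who already has another qualifying TEAE in the same table row changes nothing there.

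The conclusion assumes that no blacked-out text tells sites to enter worsening as a new AE dated at the worsening. The primary efficacy endpoint is untouched. The rule is worth correcting because it misclassifies events as written and the correction is cheap.

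**What to change.** Add one sentence to SAP 6.4.2.4, for example: *An AE or pre-existing condition that increases in severity or frequency, or becomes serious, on or after the first RBX2660 administration is treatment-emergent, with the date of worsening as its onset.*

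Implement it by one route only, so that the same worsening is not counted twice:

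- derive it in programming from the existing AE record, which requires the record to hold the date and grade of the worsening; or
- have sites enter a new AE record dated at the worsening, stated in the eCRF completion instructions and extended explicitly to AEs that began after consent.

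If a blacked-out instruction already requires the second route, the SAP need only cite it and state the onset date used.

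Cost: one SAP sentence and either a derivation rule or a completion note, with queries for AEs ongoing at the first enema if data are already in. Downside: TEAE counts may rise slightly.

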#### 4.4 Subject Withdrawal or Termination

A subject's study participation is considered complete after the final telephone call is conducted 24 months after completion of study treatment with RBX2660.

A subject may withdraw or be withdrawn from the study prematurely for the following reasons:

- Withdrawal of consent by subject
- Lost to follow-up
- Failure to comply with study requirements
- Termination of study by the sponsor
- Death
- Other (to be specified).

The reason for termination is recorded on the Study Exit eCRF. In the event that a subject withdraws from the study, every attempt should be made to have the subject return for an early withdrawal visit and to complete the 3-, 6-, 12-, and 24-month telephone calls. [REDACTED]

[REDACTED]

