4.1.5 Management of Treatment Failures

Treatment failures (as determined by the site investigator at the time of CDI recurrence) are to be treated with another therapy(ies) deemed most appropriate by their study investigator.

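### No visible rule separates adverse events after rescue therapy, and the AE percentages ignore unequal follow-up: a minor gap in the descriptive safety tables with a cheap remedy

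*SAP*

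**What the plan says.** SAP 6.4.2.4 defines a TEAE by onset date: "If the AE onset date occurs on or after initial treatment date, then the AE will be considered treatment-emergent". The branches for partial and unknown dates also test only against the start of treatment. None sets an upper limit or stops at a later therapy.

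The practical limit comes from collection. SAP 6.4.2 says of AEs in general: "Adverse events will be recorded for each subject from the day of enrollment through the 12-month phone call". For serious events and chronic disease the period is longer: "the new onset of chronic diseases will be recorded for each subject from the day of enrollment through the duration of the study". Protocol 4.4 fixes the end of the study: "A subject's study participation is considered complete after the final telephone call is conducted 24 months after completion of study treatment with RBX2660".

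Under SAP 4.1.5, treatment failures "are to be treated with another therapy(ies) deemed most appropriate by their study investigator". Treatment failure is not among the withdrawal reasons listed in Protocol 4.4, so these subjects remain in follow-up.

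SAP 8.6.1 has adverse events "summarized using counts of the number of events and frequencies (counts and percentages) of the number of subjects in the Full Analysis Set". The severity and relatedness tables use the Safety Population, which SAP 6.3 defines by any exposure to RBX2660, with no follow-up requirement. SAP 6.4.2.3 has the investigator rate each event against four possible causes: RBX2660, the enema procedure, *C. difficile* disease and a pre-existing condition. An event with no recorded rating counts as related.

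**The concern.** Two features limit what the safety tables can show.

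First, a subject who fails within 56 days and is retreated can contribute about 22 further months (730 - 56 = 674 days) of events to the RBX2660 column. If the retreatment is a fecal transplant, the subject has had two microbiota products. The SAP foresees this, because the Per Protocol definition in 6.3 names transplant before week 8. Yet no visible safety rule separates events before and after it.

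Second, the denominator is a headcount. A subject who withdraws early keeps any event already seen, but the unobserved time is in effect counted as event-free.

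Safety is a secondary objective, and SAEs and new chronic disease at 24 months are a named secondary endpoint (SAP 3.4). With a single treated arm, these percentages are the safety result. Including post-rescue events adds to the RBX2660 count, while unobserved time lowers it. The net direction is therefore unknown, and no table visible in the SAP would reveal it.

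**Working it through.** The documents state no AE rate, drop-out rate or rescue rate, so there is no plan figure to reproduce. All rates below are assumptions, used only to show the order of magnitude.

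**1. Unequal follow-up.** Assume independent event and drop-out times, each with a constant hazard. Let p be the incidence under full follow-up and d the proportion lost by the end of the window. With the window as the time unit:

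- h = -ln(1 - p) and c = -ln(1 - d)
- crude percentage = h/(h + c) x (1 - exp(-(h + c)))

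Example: p = 0.20 and d = 0.20 give h = c = 0.2231, so crude = 0.5 x (1 - 0.64) = 18.0%. The relative shortfall is 2/20 = 10%.

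| p | d | Crude | Relative understatement |
|---|---|---|---|
| 20% | 5% | 19.5% | 2% |
| 20% | 10% | 19.0% | 5% |
| 20% | 20% | 18.0% | 10% |
| 20% | 30% | 16.9% | 15% |
| 30% | 10% | 28.6% | 5% |
| 30% | 20% | 27.1% | 10% |
| 30% | 35% | 24.7% | 18% |

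The absolute loss runs from 0.5 points (20.0 - 19.5) to 5.3 points (30.0 - 24.7). Relative results are similar at p = 10% and p = 40%.

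**2. Events after rescue.** Assume a fraction f of subjects is rescued at day 28, the middle of the 56-day failure window, with a constant event hazard that rescue does not change. The share of events starting after rescue is f x (T - 28)/T.

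| f | Of 150 treated | AEs to 12 months (T = 365) | SAEs to 24 months (T = 730) |
|---|---|---|---|
| 10% | 15 | 9% | 10% |
| 20% | 30 | 18% | 19% |
| 30% | 45 | 28% | 29% |
| 40% | 60 | 37% | 38% |

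For example, 0.40 x 702/730 = 38%. These shares cover any rescue. The share after fecal transplant alone would be smaller, and the documents do not say how often it is used.

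**3. Do the other planned tables separate these events?**

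- *Relatedness tables:* partly. They separate events judged related to RBX2660 from the rest. An event caused by the rescue has no class of its own, so it must be placed under one of the four listed causes or called unrelated. A missing rating is counted as related.
- *Onset-interval tables:* possibly. SAP 8.6.1 plans AEs and SAEs by onset time, but the intervals and their denominators are redacted. Time intervals alone would not separate rescued from non-rescued subjects.

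**The case against.** The strongest reply is that counting every event after exposure, whatever happened later, is a common and conservative safety summary that keeps delayed effects visible. That stands, and it is why the all-TEAE rows should remain. SAP 8.6.1 also plans no inferential statistics for AE data, so no test or error rate is touched.

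A reader might infer more than the documents support:

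- *That post-rescue events are attributed to RBX2660.* TEAE is a timing label. Relatedness to RBX2660 is rated and tabulated separately.
- *That all AE percentages run to 24 months.* Only SAEs and new chronic disease do. Other AEs stop at the 12-month call.
- *That a subject who leaves early counts as event-free throughout.* Events before leaving are kept. Protocol 4.4 also asks for every attempt at a withdrawal visit and the later calls, which would reduce the loss.
- *That the plan certainly lacks a rescue split or exposure adjustment.* The pointer to the AE method in SAP 8.6 is redacted, as are the onset intervals, and no analysis of new chronic disease is visible. Absence cannot be confirmed.

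Two further replies carry less weight. SAP 7.1 bases percentages on non-missing subjects, and Protocol 8.5 uses available data. Neither says that a subject without an AE record leaves the denominator, and SAP 8.6.1 names the Full Analysis Set. SAP 7.1 also promises listings of all eCRF data, so timing could be recovered case by case, but a listing does not give a rate.

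**Conclusion.** The point holds as a minor one about descriptive safety. On the visible text, TEAEs are not divided at rescue, rescue has no causality class, and percentages ignore follow-up time.

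Under the assumptions above, drop-out of 5-35% understates cumulative incidence by about 2-18% in relative terms. If 10-40% of subjects were rescued near day 28, roughly 9-38% of events would start after rescue. Both ranges rest on constant hazards and on rates that the documents do not give. The redacted text could narrow the gap. Efficacy conclusions are unaffected.

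**What to change.** Unless the redacted text already covers it:

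1. **SAP 6.4.2.4:** keep the TEAE definition and add a derived flag for events with onset after the first fecal transplant, other microbiota product or CDI retreatment. Take the dates from the CDI History and On-study Episodes eCRF (Protocol 3.7) and the concomitant medication records, which SAP 6.1 has updated at every contact.
2. **SAP 8.6.1:** keep the all-TEAE rows, and show the overall TEAE, serious TEAE and new-chronic-disease summaries with and without flagged events.
3. **SAP 8.6.1, SAEs and new chronic disease:** add events per person-year, or Kaplan-Meier cumulative incidence at 12 and 24 months.

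Give the rows without flagged events person-time up to the first rescue. With an unchanged headcount they would fall simply because less time is counted. At 20% incidence over 24 months and 40% rescued at day 28, the row would show 0.6 x 20% + 0.4 x 0.85% = 12.3%. Here 0.85% is the risk by day 28, 1 - 0.8^(28/730).

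The cost is one derived variable and some added rows or columns from data already collected. The tables become longer, and the cumulative rates may be slightly higher than the crude percentages.

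### The partial-onset rules in SAP 6.4.2.4 ignore the resolution date, so an AE recorded as over before the first enema can be counted as treatment-emergent

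*SAP*

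**What the plan says.** SAP 6.4.2.4 sets out one algorithm with three branches.

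- **Complete onset date.** The date decides: "If the AE onset date is prior to initial treatment date, then the AE will not be considered treatment-emergent". Onset on or after that date makes the AE treatment-emergent.
- **Partial onset date.** With the day missing: "If day is unknown, and month/year occur on or after the first enema month/year, then the AE will be considered treatment-emergent". With month and day missing: "If month/day is unknown, and year occurs on or after first enema year, then the AE will be considered treatment-emergent". Any other partial onset is not treatment-emergent. Neither rule mentions resolution.
- **Onset wholly unknown.** Resolution decides: "If the AE resolution date is before the initial treatment date, then the AE will not be considered treatment-emergent", and "If the AE resolution date is after the initial treatment date or ongoing, then the AE will be considered treatment-emergent". If both dates are unknown, the AE is treatment-emergent.

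Collection begins before dosing. Protocol 7.1.5 states "Adverse event information is collected from the time the subject signs the Informed Consent Form", and SAP 6.4.2 states "Adverse events will be recorded for each subject from the day of enrollment through the 12-month phone call". Protocol 4.3 makes consent the point of enrollment and adds: "Subjects must discontinue their antibiotics for 24-48 hours prior to receiving the first study enema". The record can therefore hold AEs that both start and end before the first enema.

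**The concern.** An AE that has ended before the first enema cannot have begun after it. The SAP accepts this when onset is blank but drops it when the onset month or year is known. Adding correct information about onset can thus turn a right classification into a wrong one. This is an inconsistency within one algorithm, not a choice between acceptable conventions.

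At stake is the content of the TEAE summaries in SAP 8.6.1: overall, serious, by maximum severity and by relatedness. Safety is the first secondary objective, and all prospective subjects receive RBX2660, so these tables are the main safety description of the product.

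**Working it through.** The plan gives no figure to reproduce. The check applies the rule as written to test cases.

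**Inputs.** The branches of SAP 6.4.2.4 as set out above. The first enema is put at 15 June 2016 for illustration.

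**Step 1. Same resolution date, different knowledge of onset.** All AEs below resolved on 10 June 2016, five days before the enema.

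| Recorded onset | Comparison made | As written | With resolution condition |
|---|---|---|---|
| 5 June 2016 | 5 June < 15 June | not TEAE | not TEAE |
| June 2016, day unknown | June 2016 ≥ June 2016 | **TEAE** | not TEAE |
| 2016, month and day unknown | 2016 ≥ 2016 | **TEAE** | not TEAE |
| Wholly unknown | 10 June < 15 June | not TEAE | not TEAE |
| May 2016, day unknown | May 2016 < June 2016 | not TEAE | not TEAE |
| 2015, month and day unknown | 2015 < 2016 | not TEAE | not TEAE |

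Only rows two and three are wrong. The last two rows bound the problem: a partial onset in an earlier month or year is already excluded.

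**Step 2. What the condition leaves alone.** With onset June 2016 (day unknown) and resolution on 20 June, ongoing or unknown, the AE is a TEAE both as written and with the condition added.

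**Step 3. All date pairs in an assumed window.** Assume that pre-dose AEs start and end within the 30 days before the enema. This borrows the 30-day limit for baseline assessments in SAP 8.3; the screening interval itself is not readable. Each enema date gives 30 × 31 / 2 = 465 onset/resolution pairs, and the 366 dates of 2016 give 366 × 465 = 170,190 pairs. With every pair weighted equally, the share called TEAE is:

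- complete onset: 0%
- day missing: 33.4%
- month and day missing: 94.4%
- onset wholly unknown: 0%

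The year-only share can be checked by hand. A pair escapes only if onset falls in 2015. An onset *a* days before the enema does so for *a* of the enema dates and carries *a* possible resolution dates, giving 1² + 2² + … + 30² = 30 × 31 × 61 / 6 = 9,455 pairs. Then 1 − 9,455 / 170,190 = 94.4%.

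With the resolution condition added to the partial branches, both partial-onset shares fall to 0. These percentages are conditional on an AE already having a partial onset and a known pre-dose resolution. They show how the rule behaves, not how many AEs it will affect.

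**The case against.** The strongest reply is that the rule errs on the safe side and rarely operates. It can only add events to the TEAE tables, in keeping with the SAP's other defaults: both dates unknown means treatment-emergent, and missing causality means related (SAP 6.4.2.3). SAP 8.6.1 provides no inferential statistics for AEs, and listings of all AEs would expose any such record. AEs are assessed at screening and again on the day of the first enema, so recent pre-dose events are likely to have full dates. Solicited symptoms go into the diary and are summarised separately by pre- and post-treatment period (SAP 8.6.2.1). A CDI recurrence is not an AE unless it needs hospitalisation of at least 24 hours (Protocol 7.1.5). All of this stands and keeps the point small. It does not remove it: conservatism is a reason to count an event when timing is uncertain, and here the resolution date settles the timing.

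Parts of SAP section 7 are redacted and could hold a general date convention. SAP 6.4.2.4 shows no redaction and reads as complete.

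A reader might also infer more than the documents support:

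- *That the year-only rule sweeps in events that ended months before dosing.* AE collection starts at consent, and conditions already present at study start are recorded as pre-existing (Protocol 7.1.4). An event over months earlier would normally not be an AE record.
- *That many such AEs should be expected.* The documents give no frequency of missing onset days, and three conditions must coincide.
- *That tables of events related to RBX2660 or the enema are generally inflated.* Protocol 7.1.7 classes an event with no temporal relationship to product or procedure as unrelated, so those tables are affected mainly when causality is missing and defaults to related. Tables of relatedness to *C. difficile* disease or a pre-existing condition could be affected with causality recorded.

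**Conclusion.** The point holds in a narrow form. As written, SAP 6.4.2.4 misclassifies every AE that has a partial onset in the month of the first enema (or, if only the year is known, in its year) together with a known resolution before that enema. The direction is over-counting of TEAEs. Only descriptive safety tables are touched; the primary efficacy comparison is not.

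The number of such AEs cannot be derived from the documents, and the 33.4% and 94.4% above must not be read as estimates of it. The conclusion assumes that the readable text of SAP 6.4.2.4 is the whole rule and that recorded resolution dates are correct. It is a minor correction, worth making because the SAP already applies the same logic in its unknown-onset branch.

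**What to change.** Add one exception to both partial-onset rules: *unless the resolution is known to be before the initial treatment date (a complete date before it, or a known month/year wholly before the enema month/year), in which case the AE is not treatment-emergent.*

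- Leave the complete-onset rules unchanged. A resolution check placed ahead of every branch would be too broad: an AE with a complete post-dose onset and a mistyped earlier resolution date would leave the TEAE tables.
- Keep as treatment-emergent any partial-onset AE in the enema month or year whose resolution is on or after the treatment date, ongoing, unknown, or known only to the enema month (or only to the enema year). Such a resolution does not show that the event ended before dosing.
- The month/year part of the exception matters for year-only onsets. If onset is known to be in the enema month, a resolution in an earlier month contradicts it and should be queried.

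The cost is one clause in the SAP and one programming condition. There is a small downside: a wrong resolution date on a partial-onset AE could remove it from the TEAE tables. Records excluded under the new clause should therefore be queried before database lock.

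Separately, the unknown-onset branch has no rule for resolution exactly on the treatment date. The same edit could state one.
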